Subjects who meet study criteria for relapse at any point during the study will be withdrawn from the study and offered clinically-appropriate treatment as determined by the treating study physician, which may

include inpatient hospitalization, repeated administration of ketamine, electroconvulsive therapy (ECT), or other treatments determined by professional judgment. Subjects who demonstrate therapeutic benefit from experimental drug NRX-101 (DCS+ lurasidone) at study completion may be offered prescribed DCS by their treating psychiatrist.

The Schedule of Study Activities (Table 3) summarizes the frequency and timing of efficacy, PK, and safety measurements applicable to this study. With the exception of post-dose assessments, visit-specific subject-reported outcomes assessments should be conducted or completed before any tests, procedures, or other consultations for that clinic visit to prevent influencing subject perceptions. A recommended order of study procedures will be provided to sites as a separate document.

Actual dates and times of assessments will be recorded in the source documentation and electronic Case Report Form (eCRF).

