13.8 Sample Size Calculations

13.8.1 Allocation

To encourage study participation, a 2:1:1 randomization will be used where at most half as many subjects will be assigned to the lurasidone and placebo arms as compared to the K/N study arm. The goal will be to have 62 subjects randomized to K/N and 31 subjects randomized to each of K/L and K/P for a total of 124 randomized subjects. The randomization takes place among Ketamine responders once confirmed by Medical Monitor.

13.8.2 Stage 1

The study goal is to achieve a total of 124 Ketamine responders for the Stage 2 evaluation. A total of 192 subjects are projected to be enrolled but this number may be reached sooner if the cumulative effect of the Ketamine response rate exceeding 70%, if the Stage 1 loss rate being less than 8% (15 subjects), or if the Stage 2 loss rate being less than 8% (9 subjects). Thus, there would be 177 subjects who complete Stage 1 before considering Ketamine response. The literature and prior experience suggests that 70% of those treated with ketamine will have an adequate reduction in depression and suicidality which equates to 124 Ketamine responders (177×0.7) who would be available for randomization. More subjects will need to be enrolled if the Ketamine response rate was lower than 70% or the randomization refusal rate was higher than 8%, considered to be part of Stage 2 losses.

13.8.3 Stage 2

Stage 2 will investigate the study hypotheses. The primary efficacy hypothesis is that K/N will delay the time to relapse relative to K/L and K/P. The goal will be to have 62 subjects randomized to K/N and 31 subjects randomized to K/L and K/P. These numbers are based on the Ketamine Responders. See **Error! Reference source not found.** for the total number of K/N and K/L subjects required to test the primary efficacy hypothesis. The sample size requirements are shown just for K/N and K/L. .

The study is powered based on the number of subjects randomized to K/N vs. K/L. In order to achieve 90% study power with two-sided 0.05 Type I error, a total of 56 K/N subjects, 28 K/L subjects, and 28 K/P subjects must be evaluated for time to relapse over the full 6 weeks. This is based on the assumption of a 30% relapse rate in the K/N treatment group and a 70% relapse rate in the K/L and K/P treatment groups. A larger gap in the relapse rate is expected based on the literature, so this is believed to be a conservative assumption. These calculations assume a loss of 8% during Stage 2.

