13.9 Overall Type 1 Error Control

The overall Type I error is two-sided 5%. No interim analyses are planned.

A hierarchical testing plan is in place to control Type I error to extend labeling claims in the following pre-defined testing order where statistical significance (two-sided $p < 0.05$) is required at each step:

1. Primary: K/N will delay time to relapse relative to K/L and K/P
2. Secondary: K/N will separate from K/L and K/P by 72 hours, with sustained difference between groups thereafter

3. Secondary: All-cause discontinuation (including discontinuation for continued suicidal ideation) will be lower in K/N than K/L and K/P.
4. Secondary: K/N will separate from K/L and K/P starting at Day 7, with sustained difference thereafter
5. Secondary: Improvements within the K/N group observed at Week 2 will remain stable to end of study.

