13.10.4 General Methodology

Time to event analyses will be performed using a Kaplan-Meier lifetable, two-sided Wilcoxon-Gehan test, and proportional hazard models (PHREG) including the following covariates: study treatment, C-SSRS 24 hours post infusion (1,2, or 3), age (<25, 25-39, >40), and gender. The proportional hazard model results for the Intention-to-treat (ITT) population will be considered to be the primary analysis for the primary efficacy endpoint while the MMRM results for the ITT population will be considered to be the primary analysis for the secondary efficacy endpoints.

All of the instruments used to measure ASIB or depression constitute serial continuous and ordinal outcomes which will be analyzed using Mixed-Effect Model Repeated Measure (MMRM) to account for missing data and early discontinuations. The models will include treatment group, study visit, the interaction between study visit and treatment group, the baseline of the variable being analyzed, C-SSRS 24 hours post infusion (1, 2, or 3), age (<25, 25-39, >40), and gender as fixed effects. The reason for missing data will be evaluated as a condition of MMRM analysis.

An autoregressive (AR1) variance covariance structure will be assumed for this analysis. To account for mis-specification of the covariance structure, the Liang and Zeger’s “sandwich” estimator (via the EMPIRICAL option in SAS PROC MIXED) will be used. Restricted maximum likelihood (REML) will be used to estimate all parameters and will be the basis for all hypothesis testing (SAS default). For the primary model including the interaction term, the hypothesis test to perform on the fixed effects will be Type III (SAS® option htype = 3). SAS® PROC MIXED will be used.

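### The uncorrected sandwich variance makes the MMRM treatment-by-visit test reject about 12–26% of the time under no difference; the treatment and single-visit tests are only mildly inflated

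*Combined protocol and SAP*

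**What the plan says.** Section 13.10.4 makes the ITT MMRM the primary analysis of the secondary efficacy endpoints. The model has treatment, visit, their interaction, the baseline value, 24-hour C-SSRS category, age category and gender. The working covariance is AR(1). To guard against a wrong covariance, the variance is the Liang-Zeger sandwich, "via the EMPIRICAL option in SAS PROC MIXED) will be used". For the model with the interaction, "the hypothesis test to perform on the fixed effects will be Type III". Neither 13.10.4 nor 13.10.6 names a small-sample correction, a denominator-df method or another covariance.

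Section 13.9 states "The overall Type I error is two-sided 5" percent, and statistical significance "is required at each step" of the hierarchy. Steps 2 and 4 are the claims that K/N separates from K/L and K/P by 72 hours and from Day 7.

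On numbers, Section 13.8.1 says "The goal will be to have 62 subjects randomized to K/N and 31 subjects randomized to each of K/L and K/P". Section 13.8.3 assumes a "30% relapse rate in the K/N treatment group and a 70% relapse rate in the K/L and K/P treatment groups", and "These calculations assume a loss of 8% during Stage 2". Section 8.1 adds: "Subjects who meet study criteria for relapse at any point during the study will be withdrawn from the study".

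**The concern.** The sandwich is a large-sample variance. It replaces the assumed covariance with products of observed residuals, one set per subject. With few subjects those residuals are too small, because the model was fitted to the same data, and the resulting matrix is noisy. A test on one degree of freedom suffers a little. A test on many degrees of freedom suffers much more, because it inverts a large, noisy block of that matrix.

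Here each control arm starts with 31 subjects, and the later visits rest on those who have not been withdrawn. If a test named in the plan does not hold its nominal 5%, a p-value below 0.05 from it cannot be read as the plan intends, and confidence intervals from the same variance are somewhat too narrow. At stake are the secondary results on BISS, C-SSRS and CHRT.

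**Working it through.** **The plan's own figure.** Table 13 gives 90% power at effect size 0.754, two-sided 0.05. Taking 56 K/N against 28 in one comparator arm, the noncentrality is 0.754 × √(56 × 28 / 84) = 3.26. Power is 89.6% from the noncentral t with 82 df, or Φ(3.26 − 1.96) = 90.3% from the normal approximation. The figure reproduces, and it shows that step 2 was sized as a pairwise comparison. The sample size also follows: 28 / 0.92 = 30.4, rounded up to 31, and 4 × 31 = 124.

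**Inputs from the documents.** Arms of 62/31/31; the 13.10.4 covariates; AR(1) with an uncorrected sandwich; nominal 5%. Table 3 schedules BISS after randomization at Days 7, 10, 14, 21, 28, 35 and 42, so the interaction has (3 − 1) × (7 − 1) = 12 df. CHRT has five post-randomization visits, so (3 − 1) × (5 − 1) = 8 df.

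**Assumptions, not in the documents.** True covariance: AR(1) with correlation 0.7, compound symmetry 0.5, or a random intercept plus autoregression with growing variance. Share withdrawn: 0, 30, 50 or 70%, the same in all arms, either completely at random or when the score crosses a threshold. Denominator df for the interaction: within-subject, with 115 between-subject df as a variant.

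**Formulas.** With B = (Σ XᵢᵀWᵢXᵢ)⁻¹ and residuals eᵢ, the sandwich is V = B (Σ XᵢᵀWᵢeᵢeᵢᵀWᵢXᵢ) B. The test of Lβ = 0 on q df is F = (Lb)ᵀ(LVLᵀ)⁻¹(Lb) / q. No closed form gives its true size, so it was simulated: REML AR(1) fits, three identical arms, 5,000 trials per main scenario (Monte Carlo standard error about 0.3–0.6 points).

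**Results for 7 visits, plan as written, nominal 5%.**

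| Withdrawn | Left per control arm at Day 42 | Treatment × visit (within-subject df) | Treatment × visit (115 df) | Treatment (2 df) |
|---|---|---|---|---|
| 0% | 31 | 14% | 12% | 6.4–6.8% |
| 30% | 22–23 | 15–16% | 12–13% | 6.6–7.2% |
| 50% | 16–17 | 16–18% | 15–16% | 6.8–7.4% |
| 70% | 10–11 | 23–26% | 21–24% | 8.0–9.3% |

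- Single-visit K/N vs K/L contrasts: about 5–8%.
- Nine visits (16 df), interaction: 20% at 30% withdrawn, 34% at 70%. These runs had 2,000 trials each.
- Ordinal 0–5 outcome, 7 visits, interaction: 13% at 30% withdrawn, 23% at 70%, also 2,000 trials each.
- A separate run of 500 trials per scenario gave 12–23% for the 12-df test and about 4–9% for the treatment test and the visit contrasts. This is why the treatment range is stated below as about 5–9%.

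**Alternatives under the same null.**

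- Unstructured covariance with Kenward-Roger (700 trials per scenario, standard error about 0.8 points): treatment 3.7–4.6%, interaction 3.9–6.0%, last-visit K/N vs K/L 4.1–6.1%.
- AR(1) with the Mancl-DeRouen corrected sandwich: treatment 3.0–5.1%, visit contrasts 3.8–5.9%, but interaction still 10–24% with within-subject df.
- AR(1) with model-based variance: about 5% for the interaction when AR(1) is true, but the treatment test reached 17% when the truth was compound symmetric.

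**The case against.** The sandwich has a purpose. Section 13.10.4 adopts it against a wrong AR(1), and the 17% for model-based AR(1) under compound symmetry shows that the protection matters. This stands: removing EMPIRICAL and changing nothing else could make matters worse. It does not make the interaction test valid as specified.

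A reader might infer that every Type III test is badly inflated. The results do not support that. The treatment test and the visit contrasts exceed 5% by a few points at most. Nor is withdrawal the sole cause, since the interaction test is already at 12–14% with complete data. The 12 df also do not apply to every instrument: CHRT has 8, and its interaction test ran at about 8.5% with 8% dropout.

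A reader might also infer that steps 2 and 4 carry a false-claim rate of 12–26%. The documents do not say that the omnibus interaction decides either step. Both are directional claims against both comparators, reached only after the primary test succeeds, and an omnibus interaction cannot show which arm separates, when, or in which direction. With three identical arms, K/N beat both comparators at Day 7 in at most 0.7% of trials (1,200 trials per scenario). If only one comparator is null, the pairwise rate of about 5–8% applies.

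It is also tempting to simulate the null at the planned relapse and loss rates, which leave 31 × 0.30 × 0.92 = 8.6 subjects per control arm and 62 × 0.70 × 0.92 = 39.9 in K/N at Day 42. Those rates are the plan's alternative. Relapse is defined partly by the C-SSRS and the MADRS items of the BISS, so unequal relapse with identical scores is not a coherent null for those scales. The table above therefore uses equal withdrawal.

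**Conclusion.** The concern holds for one named test. For 7-visit outcomes such as BISS, the Type III treatment-by-visit test rejects roughly 12–26% of the time at nominal 5% under no difference. It is at about 12–15% with little or no withdrawal and goes higher with more visits. The Type III treatment test (about 5–9%) and the single-visit K/N vs K/L contrasts (about 5–8%) are only mildly anti-conservative.

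The direction for the interaction test was the same in every scenario run. The exact size rests on the assumed covariance, withdrawal share and denominator df, none of which the documents give. Because the plan leaves open which test or contrast decides steps 2 and 4, the interaction figure describes that test alone and not the error rate of a labeling claim. The primary proportional hazards analysis does not use this variance and is unaffected.

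**What to change.** In 13.10.4, make one change: replace AR(1) plus EMPIRICAL with an unstructured covariance, model-based REML variance and Kenward-Roger degrees of freedom, and name the fallback covariance to use if the model does not converge. Do not drop EMPIRICAL while keeping AR(1). Align 13.10.6 and Section 11 with this text.

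In 13.9, state that steps 2 and 4 rest on prespecified single-df contrasts of K/N vs K/L and K/N vs K/P at named visits, not on the omnibus interaction. The visit for the 72-hour claim needs particular care, because Table 3 has no BISS assessment between Day 1 and Day 7.

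If a robust variance is kept as a sensitivity analysis, use a bias-corrected form such as Mancl-DeRouen and limit it to those contrasts, since the correction does not repair the interaction test.

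The cost is SAP wording and a modest programming change. Standard errors will be somewhat larger, and the fallback may be needed when late visits are sparse.

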13.5.2 Secondary Efficacy Endpoints

Additionally, symptom improvement will be evaluated by assessing changes in the secondary outcome measures: C-SSRS, CHRT, BISS (MADRS), and BPRS. These measures will be assessed at the times specified on the Study Activity Schedule, Table 3.

The C-SSRS (and the retrospective C-CASA component), CHRT (CHRT-SR and CHRT-C), BISS and BPRS (including the global severity rating) will be evaluated within and between study

treatment groups. The time frame is for both lifetime and the past six months for the Baseline/Screening scale and since the last visit for the Since Last Visit scale. Mean differences will be evaluated using a paired t-test with each study group and an unpaired t-test for K/N vs. K/L and K/P.

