13.10.3 Conventions

Means, mean changes, standard deviations, and ranges will be presented separately for Stage 1 and then for each Stage 2 treatment group over time. These endpoints will be evaluated within the three study treatment groups for the change from Stage 1 and Stage 2 baselines using a paired t-test and between study treatment groups using an unpaired t-test at each time; these p-values will be presented as descriptive statistics.

For continuous variables, the mean, standard deviation, minimum, median and maximum will be presented, together with the total number of observations and the number of missing and non-missing values. Unless otherwise specified minimum and maximum values will be reported to the same number of decimal places as the recorded measurements, mean and median are reported to one more decimal place and standard deviation one additional decimal place more than the mean.

For ordinal and categorical variables, absolute and relative frequencies will be reported. Relative frequencies will be based on all observations and reported as percentages to one decimal place. Unless otherwise specified percentages will be based on the number of subjects with data and will not be calculated for missing categories.

Adverse events, medical histories and concomitant medications will be reported on a subject and an event basis. The percentages will be calculated using the number of subjects in the population Analysis Set as the denominator.

All hypotheses will be tested at 5% (final analysis) level of significance using a two-sided test unless otherwise specified.

P-values will be rounded to four decimal places. If a p-value is less than 0.0001 it will be reported as “<0.0001.” If a p-value is greater than 0.9999 it will be reported as “>0.9999”.

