16.2 Ethical Conduct of the Study

This study will be conducted in accordance with the ethical principles that have their origins in the Declaration of Helsinki, in compliance with the approved protocol, GCP and applicable regulatory requirements.

Participants must be capable of understanding the nature of this study, its potential risks, discomforts and benefits. Study physicians will obtain consent after they have fully explained the study purpose and its procedures, and potential participants have demonstrated an understanding of the protocol, willingness to participate, and competency to consent.

All subjects will receive monitoring for clinical deterioration, support, attention, and reassurance in the context of a therapeutic alliance. By definition, the target population is one in which subjects have not responded to available antidepressant therapies. Both active treatment and placebo/control groups in each trial will receive comprehensive evaluation and careful monitoring. Close monitoring by a trained psychiatrist is beneficial for individuals with mood disorders. If subjects are in need of more intensive psychiatric treatment at any time during the course of the trial, study personnel will assist in needed evaluation and referral to appropriate treatment settings. Subjects will be carefully monitored regarding depressive and other psychiatric symptoms. Non-responders to study treatment will be offered referrals for treatment at the end of the trial.

The investigators recognize that although DCS has been used in millions of individuals without report of significant safety concerns, DCS has thus far been used in 21 subjects at the 1000mg dose in formal studies of psychiatric illness. Therefore, the investigators will appoint a designated safety monitor to surveil for any safety signals that may arise in the course of the study.

Lurasidone is an FDA-approved medication which is indicated in the treatment of bipolar depression and is a member of a class of medications (5-HT_{2A} antagonists) that is routinely used in treating bipolar depression. Neither lurasidone, nor any other member of this class has successfully demonstrated efficacy against suicidality – in fact the medication bears a warning about potential suicide risk. However, its efficacy against bipolar depression is established.

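### The only inferential test named for the MMRM is a three-arm Type III test, which does not test the K/N versus K/L and K/N versus K/P claims in hierarchy steps 2 and 4

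*Combined protocol and SAP*

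**What the plan says.** Section 13.10.4 states that "the MMRM results for the ITT population will be considered to be the primary analysis for the secondary efficacy endpoints". On the model it says: "The models will include treatment group, study visit, the interaction between study visit and treatment group", plus baseline and covariates. The treatment factor has three levels, because subjects are randomized 2:1:1 to K/N, K/L and K/P. The one inferential instruction for this model is that "the hypothesis test to perform on the fixed effects will be Type III", with the matching SAS option. Section 13.10.6 repeats the model terms and adds no contrast, visit or rule for two comparators.

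Section 13.9 sets the hierarchy, "where statistical significance (two-sided $p < 0.05$) is required at each step". Step 4 reads: "Secondary: K/N will separate from K/L and K/P starting at Day 7, with sustained difference thereafter". Step 2 makes the same two-comparator claim from 72 hours.

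On pairwise tests the text is divided. Section 13.5.2 says: "Mean differences will be evaluated using a paired t-test with each study group and an unpaired t-test for K/N vs. K/L and K/P", with no descriptive label, and Section 8.2.5.1.2 is similar. Section 13.10.3 has comparisons "between study treatment groups using an unpaired t-test at each time; these p-values will be presented as descriptive statistics", and Section 11 says the same.

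**The concern.** A Type III test of treatment in this model has 2 degrees of freedom. It asks whether the three arm means, averaged over visits, are all equal. The treatment-by-visit test has 2 x (visits - 1) degrees of freedom and asks whether the arm profiles are parallel. Neither isolates K/N against one comparator, neither refers to 72 hours or Day 7, and neither has a direction. Either can be significant only because K/L differs from K/P.

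For depression that is a realistic case. Section 16.2 says of lurasidone that "its efficacy against bipolar depression is established". If K/N matches K/L on a depression scale and both beat K/P, a significant main effect could be read as passing step 2 or 4. The next labelling step would then open with no evidence that NRX-101 adds to lurasidone on that scale.

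**Working it through.** **Inputs from the documents.** Evaluable subjects 56 K/N, 28 K/L, 28 K/P (Section 13.8.3). Two-sided alpha 0.05 (Section 13.9). Step 2 effect size 0.754 at 90% power, with 0.456 just reaching significance (Table 13).

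**Assumption.** No lurasidone-placebo difference is given. It is written d, in SD units, and varied from 0.3 to 0.754.

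**1. Reproduce Table 13.** For 56 versus 28, SE = sqrt(1/56 + 1/28) = 0.2315 SD.
- Normal power: Phi(0.754/0.2315 - 1.960) = 90.3%. Noncentral t with 82 df: 89.6%. Stated: 90%.
- Just-significant effect: 1.960 x 0.2315 = 0.454 (normal) or 0.460 (t). Stated: 0.456.
- Pooling the controls (56 versus 56) gives 97.7% and does not match, although the table prints a total N of 112.

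Step 2 was therefore planned as a comparison of K/N with one comparator.

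**2. Three-arm test when K/N = K/L and both beat K/P by d, at one time point.** The overall mean is 84d/112 = 0.75d above K/P. The noncentrality is 84(0.25d)^2 + 28(0.75d)^2 = 21d^2, referred to F with 2 and 109 df. The last two columns come from 100,000 simulated trials per row.

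| d (assumed) | 21d^2 | 2-df test significant | Significant and K/N numerically best | Both contrasts favour K/N, p<0.05 |
|---|---|---|---|---|
| 0.3 | 1.89 | 21% | 10% | 1.3% |
| 0.456 | 4.37 | 44% | 22% | 2.1% |
| 0.5 | 5.25 | 51% | 26% | 2.1% |
| 0.754 | 11.94 | 87% | 44% | 2.4% |

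The last column cannot exceed 2.5%, because with K/N = K/L the K/N-K/L contrast favours K/N at two-sided 0.05 with probability 2.5%.

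**3. Repeated-measures check.** Assumptions: 8 visits, AR(1) correlation 0.6, complete data, 4,000 simulated trials per case, K/N = K/L.

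| Lurasidone effect over visits | d | Treatment main effect significant | Interaction significant |
|---|---|---|---|
| Constant | 0.456 | 85% | 5% |
| Constant | 0.754 | over 99% | 5% |
| Growing from 0 to d | 0.456 | 30% | 12% |
| Growing from 0 to d | 0.754 | 68% | 29% |

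With d = 0 both tests stay near 5%. The size of the problem therefore depends on which Type III test decides, and Section 13.10.4 does not say.

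**The case against.** The strongest reply is that the authors plainly meant pairwise comparisons. The hypotheses in Sections 5.2 and 13.4.2 are worded against both comparators, Table 13 reproduces only as pairwise, and Table 16 lists a pairwise N. The Type III line can be read as a software setting. This stands as evidence of intent, and a reader who infers that the sponsor plans to declare success on an omnibus p-value goes beyond the text. But intent does not supply a test. The analysis given primary status names no contrast, and the pairwise t-tests are called descriptive in two places.

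Three further objections narrow the point.

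- **The step 1 gate.** Steps 2 and 4 open only after step 1. If step 1 is tested pairwise, a K/N that adds nothing to lurasidone on relapse would rarely get that far. The rates above are conditional on reaching the step. They are not the overall chance of a false labelling claim.
- **The Cox model.** A reader might infer the same flaw in the primary analysis, since treatment is listed as one covariate. The documents do not support that. Type III is tied to PROC MIXED, and Sections 5.1 and 13.4.1 state the primary hypothesis as a hazard ratio against each comparator. Section 13.8.3 also assumes 70% relapse on both K/L and K/P.
- **The premise.** Section 16.2 supports a lurasidone effect on depression only. The same section, and Section 4.2, say that it has not been shown to work against suicidality. The scenario should not be extended to the C-SSRS, CHRT or SIBQ.

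Sections 6.4 and 13 promise full pre-specification in a SAP before enrolment. The statistical text available does not contain the contrasts.

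**Conclusion.** The concern holds for steps 2 and 4. The inferential test named for the MMRM cannot support a claim against both comparators, and the sections that mention pairwise t-tests disagree about their status. Given that step 1 has passed, that K/N equals K/L on the depression scale, and that lurasidone beats placebo by an assumed 0.3 to 0.754 SD, a single-time-point 2-df test is significant in about 21% to 87% of trials. If K/N must also be numerically best, this falls to 10% to 44%. Requiring both contrasts holds it to at most 2.5%. Over repeated visits, the main effect carries most of the risk. The interaction carries it only if the lurasidone effect changes with time. Step 3 has its own Wilcoxon-Gehan test and step 5 is within K/N, so neither is affected by the Type III wording.

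**What to change.** In Sections 13.10.4 and 13.10.6, replace the Type III test as the decision test for steps 2 and 4 with two MMRM contrasts, K/N-K/L and K/N-K/P. Name one depression scale (the MADRS subset of the BISS is the obvious candidate) and the scheduled visits at which the contrasts are taken. Define what sustained means at those visits, since an average over visits alone would not show it. A step passes only if both contrasts favour K/N at two-sided p<0.05. Type III tests can stay as supportive output. Align Sections 8.2.5.1.2, 11, 13.5.2 and 13.10.3 on the status of the t-tests.

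Step 2 needs a collected assessment. Table 3 has no BISS between 24 hours and Day 7, so either an assessment is added or the step is moved to a scheduled visit. If it moves to Day 7 it overlaps step 4, and the two must then be distinguished or merged.

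In Section 13.10.5, state as a clarification that the two pairwise hazard ratios are the tests.

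Apart from any added assessment, the cost is wording. At a true difference of 0.754 SD from both comparators, each single-time-point contrast has 89.6% power. The power to pass both then lies between 1 - 2 x 0.104 = 79.2% and 89.6%, and the plan should say so.
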